6.5.3. Initiation of Nucleos(t)ide Therapy Post GSK3228836 Treatment

Upon cessation of GSK3228836 treatment, participants, regardless of their baseline NA use or not, may experience virological relapse, DNA replication and an ALT flare. Investigators may, at their own discretion and in accordance with local guidelines, decide to initiate new or alternative NA therapy in these participants. Any treatment should be recorded as a concomitant medication.

6.5.4. Prohibited Medications and Non-Drug Therapies

The following concomitant medications are not permitted during the study.

- PEG-interferon or other immunomodulating therapies
- Immunosuppressing drug (e.g., prednisone) use >2 weeks duration from 3 months prior to Screening through the final Follow-up visit (see Section 5.2; unless required for safety see Section 7)
- Prior treatment with any oligonucleotide or small interfering RNA (siRNA) within 12 months prior to the first dosing
- Creatine-containing gym supplements
- Anti-coagulation therapies (e.g., warfarin, Factor Xa inhibitors or anti-platelet agents like clopidogrel).

6.6. Dose Modification

Dose modifications are not planned for this study.

6.7. Intervention after the End of the Study

No intervention is planned at the end of the study, although participants may be asked to enrol in a long-term roll-over study.

7. DISCONTINUATION OF STUDY INTERVENTION AND PARTICIPANT DISCONTINUATION/WITHDRAWAL

7.1. Discontinuation of Study Intervention

A participant may withdraw from the study treatment at any time at his/her own request or may be withdrawn at any time at the discretion of the Investigator for safety, behavioural or administrative reasons. Participants that are discontinued from treatment will enter the post-treatment period unless consent is withdrawn. Every effort should be made to complete the early termination (ET) study procedures and observations if the participant does not enter post-treatment follow-up.

Any laboratory parameter that meets the stopping criteria should be repeated to confirm the value prior to withdrawal

In rare instances, it may be necessary for a participant to permanently discontinue (definitive discontinuation) study intervention. If study intervention is definitively discontinued, the participant may remain in the study to be evaluated for safety and efficacy assessments. For participants meeting the stopping criteria (Section 7.1.1-Section 7.1.4), participants should be monitored until laboratory abnormalities resolve, stabilize, or return to within baseline values as indicated. The participant must then attend the follow-up visits specified in the SoA. See the SoA for data to be collected at the time of discontinuation of study intervention and follow-up and for any further evaluations that need to be completed.

7.1.1. Liver Chemistry Monitoring and Stopping Criteria

Liver chemistry monitoring and stopping criteria have been designed to assure participant safety and to evaluate liver event etiology. Study intervention will be discontinued for a participant if the liver stopping criteria are met. Restart/re-challenge guidelines are presented in Section 10.6.

Discontinuation of study intervention for abnormal liver tests is required when:

- a participant meets one of the discontinuation conditions outlined in Table 6
- when in the presence of abnormal liver chemistries not meeting protocol-specified stopping rules, the investigator believes study intervention discontinuation is in the best interest of the participant.

Table 6 lists the criteria for withholding or discontinuing the study medication in a study participant with elevation of ALT. Additional testing will be performed (see safety follow-up procedures for participants who meet increased monitoring or stopping criteria) and the participant monitored until liver chemistry abnormalities resolve, stabilize, or return to within baseline values. The participant must then attend the follow-up visits specified in the SoA.

Every attempt must be made to have the participant evaluated (within 24 hours) for repeat assessment of liver chemistries and additional testing and close monitoring (a specialist or hepatology consultation is recommended). Participants must be monitored twice weekly until liver chemistry abnormalities (ALT, AST, alkaline phosphatase, bilirubin)

resolve, stabilize, or return to within baseline values. Upon completion of the safety follow-up procedures (see below), the participant must attend the follow-up visits specified in the SoA.

Table 6 Liver Chemistry Monitoring and Stopping Criteria-

ALT Level	Monitoring Plan	Discontinuation
10x ULN ≤ ALT <12x ULN and Bilirubin ≤1.5x ULN and INR ≤1.5 (if available)	Monitor twice weekly Additional lab assessments	Permanently discontinue IMP if ALT >10x ULN >4 weeks
ALT ≥12x ULN and Bilirubin≤1.5x ULN and INR ≤1.5 (if available) ALT ≥3x ULN and	Hold dose Monitor twice weekly Additional lab assessments if not already done Take off hold: 150 mg SC weekly when ALT <10x ULN; increasing dose to 300 mg (if applicable) should be agreed with Medical Monitor Hold dose Monitor twice weekly Additional lab assessments if not	Permanently discontinue IMP if any of the following apply: ■ ALT ≥10x ULN >4 weeks ■ ALT ≥12x ULN recurs after IMP taken off hold Permanently discontinue IMP if the following recurs
1.5x ULN <bilirubin (="" uln="" ≤2x="">35% direct) and INR ≤1.5 (if available)</bilirubin>	already done Take off hold: 150 mg SC weekly when bilirubin returns to <1.5x ULN; increasing dose to 300 mg (if applicable) should be agreed with Medical Monitor For participants not receiving NA therapy at baseline, initiate NA therapy¹	after IMP taken off hold: 1.5x ULN <bilirubin (="" uln="" ≤2x="">35% direct) And INR ≤1.5 (if available)</bilirubin>
ALT ≥3x ULN and any of the following apply: • bilirubin >2x ULN (>35% direct) • associated with the appearance or worsening of hepatitis symptoms • INR >1.5 (if available)		Permanently discontinue IMP Monitor twice weekly until stable ALT Additional lab assessments if not already done For participants not receiving NA therapy at

ALT Level	Monitoring Plan	Discontinuation
		baseline, initiate NA therapy¹

ALT = alanine aminotransferase; IMP = investigational medicinal product; ULN = upper limit of normal 1. NA therapy may be subsequently discontinued if other tests (e.g., HBV DNA, HBsAg) rule out hepatitis B flare.

*Notes:

- Any abnormal laboratory parameters that meet the criteria for individual treatment discontinuation must be confirmed by retest of a new collection of blood samples as soon as possible.
- Deterioration considered clinically significant from the baseline in the liver parameters must be confirmed by retesting ALT, total bilirubin, direct bilirubin, and INR (if available).
- If one criterion in the list above is met and confirmed by retesting, further treatment may be discontinued for this participant after discussion with the Medical Monitor. Results of retesting must be evaluated before the next dose is administered.
- Monitor participant until liver chemistry abnormalities resolve, stabilize, or return to within baseline values.
- Cases such as Gilbert syndrome, where baseline bilirubin values are high, should be discussed with the Medical Monitor, to assess if it is a case of DILI or the participant may continue with dosing.

The procedures listed below are to be followed if a participant meets any of the liver event criteria defined in Table 6:

- Notify the Medical Monitor within 24 hours of learning of the abnormality to confirm the participant's study treatment cessation and follow-up.
- Complete the Liver Event CRF.
- Complete the "Safety Follow-up Procedures" listed below.

Safety Follow-up Procedures for Participants Who Meet *Any* of The Liver Monitoring and Stopping Criteria:

Viral hepatitis serology including:

- o Hepatitis A IgM antibody;
- o Cytomegalovirus IgM antibody;
- Epstein-Barr viral capsid antigen IgM antibody (or if unavailable, obtain heterophile antibody or monospot testing)
- o Hepatitis E IgM antibody
- o Hepatitis B virus DNA load
- Hepatitis C virus RNA load

Hepatitis D virus antibody

Obtain a blood sample for pharmacokinetic (PK) analysis as soon as possible following the occurrence of an event. Record the date/time of the PK blood sample collection and the date/time of the last dose of study treatment prior to blood sample collection on the CRF. If the date or time of the last dose is unclear, provide the participant's best approximation. Instructions for sample handling and shipping are included in the Study Reference Manual (SRM).

Serum creatine phosphokinase (CPK) and lactate dehydrogenase (LDH).

Review fractionated bilirubin

Assess eosinophilia

Record the appearance or worsening of clinical symptoms of hepatitis (fatigue, nausea, vomiting, right upper quadrant pain or tenderness, fever, rash or eosinophilia) as relevant on the Adverse Event (AE) CRF.

Record use of concomitant medications, acetaminophen, herbal remedies, other over the counter medications, or putative hepatotoxins on the Concomitant Medications CRF.

Record alcohol use on the Liver Alcohol CRF.

The following are required for participants who meet the ALT and bilirubin stopping criteria but are optional for other abnormal liver chemistries.

- Anti-nuclear antibody, anti-smooth muscle antibody, Type 1 anti-liver kidney microsomal antibodies and quantitative total immunoglobulin G (IgG or gamma globulins).
- Serum acetaminophen adduct high performance liquid chromatography (HPLC) assay (quantifies potential acetaminophen contribution to liver injury in participants with definite or likely acetaminophen use in the preceding week [James, 2009]), if available.
- Liver imaging (ultrasound, magnetic resonance, or computerized tomography) or Liver biopsy to evaluate liver disease.
- The Liver Imaging and/or Liver Biopsy CRFs are also to be completed if these tests are performed.

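### Table 6 orders no dose hold when a participant first reaches ALT ≥12x ULN with raised, mainly indirect bilirubin, although the same ALT with lower bilirubin is a mandatory hold

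*Protocol*

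**What the plan says.** Protocol Section 7.1.1, Table 6, has four rows, numbered here from the top.

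- **Row 1** is entered at "10x ULN ≤ ALT <12x ULN and Bilirubin ≤1.5x ULN and INR ≤1.5 (if available"). It asks for twice-weekly monitoring and extra laboratory tests. Its discontinuation cell reads "Permanently discontinue IMP if ALT >10x ULN >4 weeks".
- **Row 2** is entered at "ALT ≥12x ULN and Bilirubin≤1.5x ULN and INR ≤1.5 (if available"). The dose is held. Its discontinuation cell has a similar 4-week limit (ALT ≥10x ULN) and also stops treatment permanently if ALT ≥12x ULN recurs. Its release rule, "Take off hold: 150 mg SC weekly when ALT <10x ULN", does not mention bilirubin.
- **Row 3** is entered at ALT ≥3x ULN with bilirubin above 1.5x and up to 2x ULN, more than 35% direct, and INR ≤1.5 if available. The dose is held. The only permanent stop is for recurrence after release.
- **Row 4** is entered at ALT ≥3x ULN with any one of "bilirubin >2x ULN (>35% direct"), new or worse hepatitis symptoms, or INR >1.5. It is a permanent stop.

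The 24-hour Medical Monitor notification, the Liver Event CRF and the safety work-up depend on meeting a row: "The procedures listed below are to be followed if a participant meets any of the liver event criteria defined in Table 6".

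The text before the table also requires twice-weekly monitoring until liver tests resolve or stabilise, and every attempt at evaluation within 24 hours. Neither is tied to a particular row.

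**The concern.** Row 2 holds the dose on ALT alone, even when bilirubin is normal. A higher bilirubin gives no reason to withdraw that protection, whatever its fraction. Yet the entry conditions do withdraw it: rows 1 and 2 close once bilirubin passes 1.5x ULN, and the bilirubin limbs of rows 3 and 4 open only above 35% direct. A participant with a large ALT rise and a mainly indirect bilirubin rise falls between them.

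The state is possible in this trial. Exclusion criterion 18e lets participants with benign unconjugated hyperbilirubinaemia be considered after discussion with the Medical Monitor. ALT flares are expected, and ALT increase is an adverse event of special interest. Section 4.3 gives a plasma and tissue half-life of about 3 weeks, so a dose given when it should have been held cannot quickly be undone.

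There is also a reporting consequence. SAP Section 4.5.3.1 takes its liver monitoring and stopping events from protocol Section 7.1.1. A participant who meets no row may therefore be missing from those displays, although the ALT value would still appear in the laboratory summaries.

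**Working it through.** The plan gives no figure to reproduce. The question is whether the four rows cover every state with ALT ≥10x ULN.

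**Specific cases** (INR 1.1, no symptoms)

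| ALT (x ULN) | Bilirubin (x ULN) | Direct | Row now | Mandatory dosing action now |
|---|---|---|---|---|
| 15 | 1.4 | 30% | 2 | Hold |
| 15 | 1.6 | 30% | none | None |
| 15 | 1.6 | 40% | 3 | Hold |
| 15 | 2.5 | 30% | none | None |
| 15 | 2.5 | 40% | 4 | Permanent stop |
| 11 | 1.4 | 30% | 1 | No hold; 4-week limit |
| 11 | 1.6 | 30% | none | No hold; 4-week limit unclear |

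At ALT 15x ULN and 30% direct, a bilirubin rise from 1.4x to 1.6x ULN removes the hold. At ALT 11x ULN no hold is lost, because row 1 has none.

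**Coverage check.** The four entry conditions were evaluated on this grid:

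- ALT 10, 11, 12, 15, 20 x ULN (5 values)
- bilirubin 1.0, 1.4, 1.5, 1.6, 2.0, 2.5, 3.0 x ULN (7)
- direct fraction 20, 30, 35, 36, 40, 60% (6)
- INR unavailable, 1.1, 1.6 (3)
- symptoms no, yes (2)

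Total: 5 × 7 × 6 × 3 × 2 = 1,260 combinations.

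The unmatched ones all have bilirubin above 1.5x ULN (4 values), direct ≤35% (3), INR ≤1.5 or unavailable (2) and no symptoms (1):

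- all ALT values: 5 × 4 × 3 × 2 × 1 = 120
- ALT 10 to <12x ULN: 2 × 4 × 3 × 2 × 1 = 48
- ALT ≥12x ULN, where the hold is missing: 3 × 4 × 3 × 2 × 1 = 72

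**The 4-week limit.** Section 7.1.1 requires discontinuation when a discontinuation condition in Table 6 is met. The 4-week conditions are worded on ALT alone, so they can be read as applying to anyone. They also sit in rows entered only at bilirubin ≤1.5x ULN, so they can be read as applying only there. The text does not settle this. Under the second reading row 3 also lacks the limit. On the grid, 5 ALT × 2 bilirubin (1.6, 2.0) × 3 direct (36, 40, 60%) × 2 INR × 1 symptom level = 60 combinations fall in row 3 alone.

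**After the fix.** With the bilirubin condition removed from rows 1 and 2 and the strictest action applied, 0 of 1,260 are unmatched: 48 go to row 1 and 72 to row 2. None of the other 1,260 − 120 = 1,140 changes its immediate action (monitor, hold or stop). The 60 row 3 combinations gain an explicit 4-week limit.

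**The case against.** The strongest reply is that the protocol has other protection, and that the state is narrow.

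- **Investigator discretion.** Section 7.1.1 requires a stop when, with "abnormal liver chemistries not meeting protocol-specified stopping rules, the investigator believes study intervention discontinuation is in the best interest" of the participant. This stands as a softener, but it rests on judgement and orders no hold.
- **Gilbert-type cases.** The Table 6 notes send cases with a high baseline bilirubin to the Medical Monitor to decide whether dosing may continue. This covers part of the likely population. It does not cover bilirubin that rises newly on study, and it sets neither a hold nor a time limit.
- **Retesting.** "Results of retesting must be evaluated before the next dose is administered" may delay a dose, but it sits in the note about a criterion already met and confirmed.
- **NA initiation.** Section 6.5.1 starts NA in this state for participants not on it at baseline. It does not hold study drug.
- **Symptoms.** Any new or worse hepatitis symptom leads to row 4. This stands and narrows the gap.

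A reader might infer two stronger things. One is that liver monitoring lapses. It does not, because twice-weekly monitoring is required outside the table. The other is that the 4-week stop is definitely lost. The text supports only that its application is unclear. A participant already in row 1 or 2 whose bilirubin rises later arguably keeps the hold and the clock, so the point concerns first entry.

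**Conclusion.** The gap is in the text. What is clearly lost is the mandatory hold at ALT ≥12x ULN, and from ALT 10x ULN the Table 6-linked Medical Monitor notification and Liver Event CRF. Whether the 4-week stop applies is ambiguous. At the same ALT, the mandated action can be weaker when bilirubin is higher.

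This rests on reading the entry conditions as printed, with row 3 covering bilirubin above 1.5x and up to 2x ULN at more than 35% direct. The grid counts depend on the values chosen and show logic, not risk. The documents do not say how many participants would reach this state. It is probably few, because total bilirubin above 1.25x ULN is excluded at entry apart from benign unconjugated cases discussed with the Medical Monitor. The point is worth fixing because it concerns a safety action and the remedy is short.

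**What to change.** Amend protocol Section 7.1.1, Table 6:

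1. Remove the bilirubin ≤1.5x ULN condition from the entry to rows 1 and 2.
2. State that when more than one row is met, the strictest action applies.
3. State that permanent discontinuation for ALT ≥10x ULN lasting more than 4 weeks applies whatever the bilirubin level or direct fraction, including in row 3. Without this, an indirect pattern in row 2 would have a 4-week stop while the more serious direct pattern in row 3 might not.
4. Add to row 2 that if bilirubin is still >1.5x ULN when ALT falls below 10x ULN, release from hold must be agreed with the Medical Monitor.

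The cost is an amendment with IRB/IEC approval, and possibly a few extra holds, stops or Medical Monitor calls in benign indirect hyperbilirubinaemia. No new test is needed, because total, indirect and direct bilirubin are already in the chemistry panel (Appendix 2, Table 13).

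The SAP version history lists analyses requested at the third interim, which was planned for when all participants had completed Week 24. Dosing may therefore be over, although the documents do not show this directly. If so, carry the wording into any successor protocol.

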2.3.1. Risk Assessment

Risks are summarized in Table 5. Additional withdrawal/stopping criteria for liver chemistry monitoring, drug induced vascular injury (DIVI), hematology, renal function, and PK are discussed in Section 7. Planned dose adjustments for individuals for safety are outlined in Section 6.6.

Table 5 Summary of Potential Risks of Clinical Significance

Potential Risk of Clinical Significance	Summary of Data/Rationale for Risk	Mitigation Strategy					
Investigational Product (IP) [e.g., GSK3228836]							
Nonclinical Risks:	Inflammatory and immune changes are recognized as a	Laboratory Evaluations: Inclusion of biomarker panels to					
Drug Induced Vascular Inflammation and Complement Activation	class effect of antisense oligonucleotide (ASOs). Vasculitis and/or perivascular inflammation has been described in monkey studies with many if not most ASOs.	look for inflammatory and immune activation that would be expected to accompany vascular injury					
	This effect has not been observed in clinical studies with GSK3228836 to date.	Stopping Criteria: Proposed Monitoring Schedule and Stopping Rules for Drug Induced Vascular Injury and Complement Activation (see Section 7.1.2)					
Clinical Risks:	•						
Drug induced liver injury / ALT Flares	The liver is a site of accumulation of antisense oligonucleotides. Liver findings in nonclinical studies of GSK3228836 were generally limited to mild hepatic enzyme elevations associated with hepatic vacuolation without concomitant histologic evidence of degeneration in mice, consistent with findings noted with other 2'-methoxyethyl (MOE) ASOs. Review of the available clinical data indicates liver enzymes are increased on treatment with ASOs in a low percentage of patients compared to placebo. ALT elevations (defined as ALT ≥ 2X ULN) associated with HBsAg reductions were observed in 8 out of 18 treatment-naïve participants in the ISIS 505358-CS3 study (150 mg GSK3228836, N=6; 300 mg GSK3228836, N=12). Among the 8 participants with ALT flares, 6 achieved >1 log HBsAg reduction, another 2 had >0.5 log HBsAg reduction.	Laboratory Evaluations: hepatic enzyme monitoring as presented in Table 6 Stopping Criteria: ALT flares are expected in the study population. Monitoring and stopping criteria are presented in Section 7.1.1					

Potential Risk of Clinical Significance	Summary of Data/Rationale for Risk	Mitigation Strategy

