4. STUDY DESIGN

4.1. Overall Design

This is a Phase 2b, multi-center, randomized, partial-blind [Sponsor and Participant blinded], study to assess efficacy and safety of treatment with GSK3228836 in two populations of patients with CHB (1) participants on stable nucleos(t)ide treatment and (2) participants not currently on nucleos(t)ide therapy.

Both populations of patients with CHB will be randomized into one of 4 parallel arms:

- 300 mg GSK3228836 once/week for 24 weeks (plus loading dose of 300 mg GSK3228836 on Day 4 and Day 11);
- 300 mg GSK3228836 once/week for 12 weeks (plus loading dose of 300 mg GSK3228836 on Day 4 and Day 11) followed by step-down in dose of 150 mg (plus placebo to match to maintain participant blinding) GSK3228836 once/week for 12 weeks;
- 300 mg GSK3228836 once/week for 12 weeks (plus loading dose of 300 mg GSK3228836 on Day 4 and Day 11) followed by placebo once/week for 12 weeks;
- Placebo once/week for 12 weeks followed by 300 mg GSK3228836 once/week for 12 weeks (plus placebo loading doses to match on Day 4 and Day 11, no loading dose for GSK3228836 treatment)

After the 24 weeks of dosing with GSK3228836 or placebo, there will be a post-treatment follow-up period of 24 weeks.

Populations will be stratified based on HBsAg level (HBsAg \leq 3 log IU/mL and \geq 3 log IU/mL) and whether participants are HBeAg positive or negative.

The study is a partially blinded study where participants will be blinded to the study treatment. The investigators, site staffs and pharmacist will be unblinded. GSK and contract research organization (CRO) team members will be blinded to participants' study treatment and any potentially unblinding information, unless specified otherwise in the study blinding management plan (e.g., unblinded site monitors).

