4.2.4. Additional estimands

The following supplementary estimands are defined to support the primary objective.

4.2.4.1. Using Hypothetical Strategy to Deal with ICE of Discontinuation of, Interruption of, and Adherence to IP

The first supplementary estimand is defined in the same way as the primary estimand, except the intercurrent event of discontinuation of, interruption of, and adherence to IP will be handled assuming they had not happened (hypothetical strategy). Discontinuation of GSK3228836 or significant interruption/non-adherence to GSK3228836 will be handled assuming the intercurrent event had not happened (hypothetical strategy). Significant interruption/non-adherence is defined as a gap of >=21 days between treatment doses at any time during the on-treatment period. According the hypothetical strategy, any data collected after the intercurrent event will be set to missing.

This supplementary estimand supporting the primary objective in participants with CHB on stable nucloes(t)ide therapy and participants with CHB not currently on nucleos(t)ide therapy is the proportion of participants in each treatment arm 1, 2, 3 and 4 who achieve SVR for 24 weeks after the planned end of GSK3228836 treatment in the absence of rescue medication, had they not been affected by discontinuation of IP, interruptions in IP, adherence to IP, or wide disruptive events.

4.2.4.2. Measuring SVR from Actual End of Treatment instead of Planned End of Treatment

The second supplementary estimand is defined in the same way as the primary estimand, except the assessment time frame for participants achieving SVR will be 24 weeks after the actual end of treatment. Therefore, the strategy for intercurrent events of treatment discontinuation will be while-on-treatment. This supplementary estimand supporting the primary objective in participants with CHB on stable nucleos(t)ide therapy and participants with CHB not currently on nucleos(t)ide therapy is the proportion of participants in each treatment arm 1, 2, 3 and 4 who achieve SVR for 24 weeks after the actual end of GSK3228836 treatment in the absence of rescue medication, regardless of completing IP, interruptions in IP or adherence to IP, had they not been affected by wide disruptive events.

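### Protocol Table 6 brings held participants back at 150 mg weekly whatever their arm or phase, which read literally puts active drug into the Arm 3 and Arm 4 placebo phases; Sections 2.3.1 and 6.6 do not agree with it

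*Protocol*

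**What the plan says.** Protocol Section 7.1.1 introduces the table in general terms: "Table 6 lists the criteria for withholding or discontinuing the study medication in a study participant with elevation of ALT". Two of its four rows hold the dose and then release it.

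- ALT row (ALT at least 12x ULN, bilirubin and INR not raised): "Take off hold: 150 mg SC weekly when ALT <10x ULN; increasing dose to 300 mg (if applicable) should be agreed with Medical Monitor".
- Bilirubin row (ALT at least 3x ULN, bilirubin above 1.5x and up to 2x ULN): "Take off hold: 150 mg SC weekly when bilirubin returns to <1.5x ULN", with the same proviso about a later increase to 300 mg.

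Section 4.1 assigns Arm 3 twelve weeks of 300 mg "followed by placebo once/week for 12 weeks". Arm 4 has the reverse order, with placebo in Weeks 1-12 and 300 mg in Weeks 13-24.

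Three other places deal with dose changes:

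- Section 6.6: "Dose modifications are not planned for this study".
- Section 2.3.1: "Planned dose adjustments for individuals for safety are outlined in Section 6.6".
- The synopsis (Section 1.1) rules out group dose adjustments and places individual safety adjustments in the monitoring and stopping criteria.

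**The concern.** A liver hold is a point at which a site looks up what to give next. Here the table answers with a single active dose, although two of the four arms each spend half the dosing period on placebo. If the instruction were followed as written in those phases, participants would receive investigational drug that their arm does not assign, shortly after a liver event.

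Two analyses would be touched. Arm 3's SVR is assessed from Week 12 on the premise that GSK3228836 has stopped. Arm 4's Weeks 1-12 are the comparator for the exploratory safety biomarkers (Protocol Section 4.2.2), one period of the by-week safety displays (SAP Section 4.5) and the concurrent placebo for any historical borrowing (SAP Section 4.3.2).

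A hold during Arm 3's placebo phase cannot be dismissed. Section 6.5.3 says that participants who stop GSK3228836 "may experience virological relapse, DNA replication and an ALT flare".

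**Working it through.** The plan states no figure to reproduce here. The check is a comparison of passages, with some simple counts.

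**1. What a 150 mg dose is.** Section 6 counts placebo as study intervention, so a placebo phase falls under Table 6. In Section 6.1 a 150 mg dose is one active injection plus one placebo injection, and placebo has no milligram strength. The off-hold dose therefore cannot be read as a placebo dose.

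**2. Whether an exception exists.** The notes to Table 6 contain none for arm or phase. Section 7.1.5 sends treatment on hold back to Sections 7.1.1-7.1.4 and adds none.

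**3. The literal rule against Section 4.1.**

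| Arm | Weeks 1-12 assigned | Weeks 13-24 assigned | Literal effect of resuming at 150 mg |
|---|---|---|---|
| 1 | 300 mg | 300 mg | Reduction in both phases |
| 2 | 300 mg | 150 mg | Reduction, then the assigned dose |
| 3 | 300 mg | Placebo | Reduction, then active drug in place of placebo |
| 4 | Placebo | 300 mg | Active drug in place of placebo, then reduction |

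**4. Overlap with Arm 3's SVR windows (SAP Table 3).** The Schedule of Activities puts the twelve placebo-phase doses weekly from Day 85 to Day 162.

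| Window | Study days | Scheduled doses falling inside |
|---|---|---|
| End of treatment | 64-98 | 2 (Days 85, 92) |
| Post-treatment Week 8 | 99-154 | 8 (Days 99 to 148) |
| Post-treatment Week 16 | 155-210 | 2 (Days 155, 162) |
| Post-treatment Week 24 | 211-266 | 0 |

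The sum is 2 + 8 + 2 + 0 = 12. Counting dosing days only, the overlap is the end of the first window, all of the second and the first days of the third.

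**5. Upper limits.**

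- Arm sizes: 440/2 = 220 per population. At 3:3:3:1 this gives 220 x 3/10 = 66 and 220 x 1/10 = 22, matching Protocol Section 9.2.
- Participants with a placebo phase: 2 x (66 + 22) = 176, and 176/440 = 40%.
- Arm 3 planned active dose: (12 + 2) x 300 = 4,200 mg. One 150 mg dose adds 150/4,200 = 3.6%. The extreme is 12 x 150 = 1,800 mg extra, giving 6,000 mg.
- Arm 4 planned active dose: 12 x 300 = 3,600 mg. One 150 mg dose adds 150/3,600 = 4.2%. At most 11 weekly doses can follow a hold in Weeks 1-12, because the first dose precedes any hold: 11 x 150 = 1,650 mg extra.
- One Arm 3 participant whose response status changed would move that arm's observed rate by 1/66 = 1.5 percentage points.

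These are ceilings and unit effects. They do not estimate how many participants are affected.

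**6. The statements on dose modification.** Section 2.3.1 points to Section 6.6. Section 6.6 lists no adjustment and says none is planned. The synopsis points to the stopping criteria, where Table 6 does contain one. The synopsis and Table 6 agree with each other; Sections 2.3.1 and 6.6 agree with neither.

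**The case against.** The strongest reply is that nobody would follow the table literally. Section 4.1 fixes placebo for these phases. Investigators, site staff and pharmacists are unblinded, and Section 7.1.1 requires the Medical Monitor to be told of any Table 6 event within 24 hours. This stands as a reason not to predict misdosing. It does not cure the text. The notification concerns stopping and follow-up, and Medical Monitor agreement is tied only to the increase to 300 mg. SAP Section 4.8 records that some participants started nucleos(t)ide therapy on Day 1 after a misunderstanding of the protocol, so unclear instructions have been acted on in this trial.

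The second reply is that the synopsis explains Table 6: no group adjustments, individual ones in the stopping criteria. That largely answers the conflict with Section 6.6. What remains is that 6.6 is unqualified and the reference in 2.3.1 leads to nothing.

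The third reply concerns SVR. Section 6.5.3 names virological relapse together with the flare, and the SAP takes the worst value in each post-treatment window, so many such participants would already be non-responders. In the bilirubin row, participants not on nucleos(t)ides at baseline must start them, and therapy begun for antiviral suppression counts as non-response. This stands, and it limits the likely bias.

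Several stronger readings are tempting, but the documents do not support them:

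- **Arm 3's SVR would be measured on treatment throughout Days 99-266.** Dosing ends at Day 162, and the last window contains no dose.
- **The 176 participants are those affected.** They are everyone with a placebo phase; the relevant group is those held and then resumed within it.
- **A reduced Arm 1 participant receives exactly Arm 2's regimen.** The totals match at 14 x 300 + 12 x 150 = 6,000 mg only if the reduction starts at Week 13 with no dose missed. One held 300 mg dose gives 5,700 mg, and an increase back to 300 mg can be agreed.
- **SAP Section 4.2.4.1 must treat a dose change as an intercurrent event.** That supplementary estimand covers discontinuation and interruption: "Significant interruption/non-adherence is defined as a gap of >=21 days between treatment doses". Extending it would set to missing the data after a protocol-directed reduction, which may follow a flare linked to HBsAg decline. Keeping such participants as randomised fits the primary treatment-policy strategy.

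**Conclusion.** The inconsistency is real and is a matter of text. As written, Table 6 instructs active dosing after a hold in phases where Section 4.1 assigns placebo, and Section 2.3.1 relies on a Section 6.6 that denies the adjustments exist. It is a stated rule that conflicts with the design, not merely an omitted detail.

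The size of the effect is unknown. The documents give no rate of holds at these thresholds, in placebo phases or elsewhere. The nearest figures, from the earlier four-week study, are for ALT of at least 2x and at least 3x ULN, well below the 12x of the ALT row. Any effect on Arm 3 would be confined to the windows identified above and to participants whose response status changed. The Arm 4 comparisons are described in the protocol as unpowered, and the biomarker comparison is exploratory. The point calls for clarification; it does not by itself call the primary estimates into question.

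The conclusion assumes only that Table 6 means what it says and applies to every participant. It makes no assumption about what sites did, and takes no view on which dose or rule is right.

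**What to change.** Reconcile Table 6, Sections 2.3.1, 4.1 and 6.6 and the synopsis, so that the off-hold instruction is stated consistently for each arm and each phase, explicitly including the placebo phases of Arms 3 and 4. The sponsor decides its content. The cost is a short protocol clarification.

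Dosing may already be over: SAP amendment 01 (11 February 2022) includes analyses requested at the third interim, which the protocol places after all participants complete Week 24. If so, check the existing dose records and list any active dose given in a placebo phase after a hold, by arm and study day. The SAP already provides for cumulative dose by dose level (Section 4.5.1), dose compliance (Section 6.1.5) and hold/stopping profiles with administration details (Section 4.5.3.1), so the listing needs no new data collection. No change to the SAP Section 4.2.4.1 estimand is required.
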